12.4.1. Chemistry

- Hepatic function panel including alanine aminotransferase, aspartate aminotransferase, alkaline phosphatase, total and direct bilirubin, and albumin.
- Basic metabolic panel including BUN and creatinine.

12.4.2. Serum virologic testing

- HCV RNA (with Genotyping per protocol)
- Hepatitis B surface antigen
- HIV antibody testing.
- HBV Core Antibody (as needed)

12.4.3. Pregnancy Testing

Blood and urine pregnancy tests will be performed (as appropriate) per the schedule of procedures (section 5.2).

12.4.4. Hepatitis C Viral Kinetics

Each time standard of care laboratories are drawn, subjects may have one additional purple -top tube drawn (4cc of blood). This blood test is optional. The research coordinator will process the tube and store it in a -80° freezer in the Perelman Center for Advanced Medicine 7th Floor Gastroenterology Research Office. Each month, these tubes will be shipped to Abbott Pharmaceuticals so they can test for HCV antibodies, HCV core antigen, and HCV RNA. These additional tests will be included in the informed consent process for all subjects. Abbott will perform these tests free of charge to University of Pennsylvania once both are able to reach a Material Transfer Agreement (MTA).

12.5. Zepatier Related Laboratory Abnormalities and Drug Interactions

Laboratory Abnormalities

The following laboratory abnormalities were observed in studies done with Zepatier:

Late elevations in aminotransferase levels greater than 5 times the upper limit of normal generally occurred in around 1-3% of patients in previous Zepatier clinical trials; these increases were rarely associated with hyperbilirubinemia. These abnormalities were reversible and had no major clinical consequences.

Effects of Zepatier on antiretrovirals:

- Atazanavir/ritonavir 300/100mg co-administered with MK-5172 200mg daily somewhat increased atazanavir exposure (AUC increased 43%, Cmax increased 12%, C24 increased 23%). Co-administration of these medications is not recommended.

- Darunivir/ritonavir 600/100 mg co-administered with MK-5172 200 mg was not significantly altered by either MK-5172 or MK-8742. However, due to DRV/r effects on Zepatier exposure, co-administration is not recommended.
- Efavirenz was not significantly impacted when co-administered with Zepatier, though it may negatively impact Zepatier exposure.
- Lopinavir/ritonavir exposures were not significantly impacted when co-administered with Zepatier. However, due to LPV/r effects on Zepatier exposure, co-administration is not recommended.

Effect of Antiretrovirals on Zepatier:

- Atazanavir/ritonavir 300/100mg co-administered with MK-5172 200mg significantly increased exposure of MK-5172 (AUC increased 10.58-fold, Cmax increased 6.24-fold, and C24 increased 11.6-fold). These findings were similar when ATV/r was combined with 50mg MK-8742. MK-8742 AUC geometric mean ratio (GMR) was 4.76, probably due to ATV/r CYP3A4/Pgp inhibition and possible inhibition of OATP-mediated disposition of MK-8742. Co-administration of these medications is not recommended.
- Exposures of MK-5172 were significantly increased when MK-5172 200 mg was co-administered with darunavir/ritonavir 600/100 mg daily. MK-5172 AUC increased 7.5-fold, Cmax increased 5.27-fold, and C24 increased 8-fold. MK-8742 exposures were also significantly increased when combined with DRV/r 600/100 mg daily. MK-8742 AUC GMR following co-administration was 1.66. This increase is likely caused by CYP3A4/Pgp inhibition by DRV/r and possibly inhibition of OATP-mediated disposition of MK-8742. For these reasons, co-administration of Zepatier and DVR/r is not recommended.
- Efavirenz 600mg co-administration with MK-5172 200 mg decreased MK-5172 AUC by 84%, most likely due to CYP3A4 induction. The same dose EFV combined with MK-5172 50 mg also decreased MK-8742 AUC 54% for the same reasons. Co-administration of these medications may cause sub-therapeutic MK-5172 exposure.
- Lopinavir/ritonavir 400/100 mg co-administered with MK-5172 200 mg significantly increased MK-5172 exposure. MK-5172 AUC increased 12.86-fold, Cmax increase 7.31-fold, and C24 increased 21.7-fold. When the same dose of LPV/r was administered with MK-8742 50 mg, MK-8742 AUC GMR was increased to 3.71. LPV/r likely impacts MK-8742 exposures due to CYP3A4/Pgp inhibition and possible inhibition of OATP-mediated disposition. Co-administration of these medications is not recommended.

Effect of Zepatier on Other Drugs:

- Rosuvastatin 10 mg co-administered with Zepatier 200/50 mg increased rosuvastatin exposure. Rosuvastatin AUC and Cmax were increased 59% and 325% respectively when exposed to MK-5172 alone and 126% and 449% when exposed to the combined Zepatier pill. The most likely cause of the increase is pre-systemic inhibition of rosuvastatin efflux in the liver and/or gut due to BCRP inhibition. Clinicians may want to avoid co-administration of Zepatier and rosuvastatin.
- Midazolam 2 mg/mL combined with multi-dose MK-5172 200 mg daily decreased midazolam AUC to 34%. MK-5172 is likely a weak CYP3A4 inhibitor.
- Multiple oral doses of rifampin did not significantly affect MK-5172 AUC, but reduced C24h by 85%. This decrease was presumably due to the combined effect of OATP inhibition and CYP3A4/Pgp induction by chronic rifampin administration. Clinicians should avoid co-administration of these medications until further data becomes available.

Effect of Other Drugs on Zepatier:

- Rosuvastatin 10 mg co-administered with Zepatier 200/50 mg did not significantly alter MK-5172/8742 exposure. However, due to Zepatier effects on rosuvastatin exposure, clinicians may wish to avoid co-administration.

- Ketoconazole (CYP3A4 and P-gp inhibitor) approximately tripled MK-5172 AUC. In healthy male subjects taking 400 mg multi-dose ketoconazole, MK-8742 AUC increased by 31%.
- Combining MK-5172 200 mg and a single dose of 600 mg IV rifampin caused a 12.6-fold increase in MK-5172 AUC, compared to an 8.35-fold increase with a single dose of oral rifampin 600 mg. This is likely due to P-gp and OATP inhibition by rifampin. Clinicians should avoid co-administration of these medications until further data becomes available.

12.6. Epclusa Related Laboratory Abnormalities and Drug Interactions

Effects of Epclusa on Other Drugs:

- Velpatasvir is an inhibitor of drug transporters P-gp, breast cancer resistance protein (BCRP), OATP1B1, OATP1B3, and OATP2B1. Coadministration of Epclusa with drugs that are substrates of these transporters may increase the exposure of such drugs.
- Fluctuations in INR values may occur in patients receiving warfarin concomitant with HCV treatment, including treatment with Epclusa. Frequent monitoring of INR values is recommended during treatment and post-treatment follow-up.

Effects of Other Drugs on Epclusa:

- Sofosbuvir and velpatasvir are substrates of drug transporters P-gp and BCRP while GS-331007 (the predominant circulating metabolite of sofosbuvir) is not. In vitro, slow metabolic turnover of velpatasvir by CYP2B6, CYP2C8, and CYP3A4 was observed.
- Drugs that are inducers of P-gp and/or moderate to potent inducers of CYP2B6, CYP2C8, or CYP3A4 (e.g., rifampin, St. John's wort, carbamazepine) may decrease plasma concentrations of sofosbuvir and/or velpatasvir, leading to reduced therapeutic effect of Epclusa. The use of these agents with Epclusa is not recommended. Epclusa may be coadministered with P-gp, BCRP, and CYP inhibitors.

Established and Potentially Significant Drug Interactions:

- See Table on next page.

Table: Potentially Significant Drug Interactions: Alteration in Dose or Regimen May Be Recommended Based on Drug Interaction Studies or Predicted Interaction^a

Concomitant Drug Class: Drug Name	Effect on Concentration ^b	Clinical Effect/Recommendation
Acid Reducing Agents:	↓ velpatasvir	Velpatasvir solubility decreases as pH increases. Drugs that increase gastric pH are expected to decrease concentration of velpatasvir.
Antacids (e.g., aluminum and magnesium hydroxide)		Separate antacid and EPCLUSa administration by 4 hours.
H ₂ -receptor antagonists ^c (e.g., famotidine)		H ₂ -receptor antagonists may be administered simultaneously with or 12 hours apart from EPCLUSa at a dose that does not exceed doses comparable to famotidine 40 mg twice daily.
Proton-pump inhibitors ^c (e.g., omeprazole)		Coadministration of omeprazole or other proton-pump inhibitors is not recommended. If it is considered medically necessary to coadminister, EPCLUSa should be administered with food and taken 4 hours before omeprazole 20 mg. Use with other proton pump- inhibitors has not been studied.
Antiarrhythmics: amiodarone	Effect on amiodarone, sofosbuvir, and velpatasvir concentrations unknown	Coadministration of amiodarone with EPCLUSa may result in serious symptomatic bradycardia. The mechanism of this effect is unknown. Coadministration of amiodarone with EPCLUSa is not recommended; if coadministration is required, cardiac monitoring is recommended [see Warnings and Precautions (5.1) and Adverse Reactions (6.2)].
digoxin ^c	↑ digoxin	Therapeutic concentration monitoring of digoxin is recommended when coadministered with EPCLUSa. Refer to digoxin prescribing information for monitoring and dose modification recommendations for concentration increases of less than 50%.
Anticancers: topotecan	↑ topotecan	Coadministration is not recommended.
Anticonvulsants: carbamazepine phenytoin phenobarbital oxcarbazepine	↓ sofosbuvir ↓ velpatasvir	Coadministration is not recommended.
Antimycobacterials: rifabutin rifampin ^c rifapentine	↓ sofosbuvir ↓ velpatasvir	Coadministration is not recommended.
HIV Antiretrovirals:		
efavirenz ^c	↓ velpatasvir	Coadministration of EPCLUSa with efavirenz-containing regimens is not recommended.
Regimens containing tenofovir DF	↑ tenofovir	Monitor for tenofovir-associated adverse reactions in patients receiving EPCLUSa concomitantly with a regimen containing tenofovir DF. Refer to the prescribing information of the tenofovir DF-containing product for recommendations on renal monitoring.
tipranavir/ritonavir	↓ sofosbuvir ↓ velpatasvir	Coadministration is not recommended.
Herbal Supplements: St. John's wort (Hypericum perforatum)	↓ sofosbuvir ↓ velpatasvir	Coadministration is not recommended.
HMG-CoA Reductase Inhibitors: rosuvastatin ^c	↑ rosuvastatin	Coadministration of EPCLUSa with rosuvastatin may significantly increase the concentration of rosuvastatin, which is associated with increased risk of myopathy, including rhabdomyolysis. Rosuvastatin may be administered with EPCLUSa at a dose that does not exceed 10 mg.
atorvastatin	↑ atorvastatin	Coadministration of EPCLUSa with atorvastatin is expected to increase the concentrations of atorvastatin, which is associated with increased risk of myopathy, including rhabdomyolysis. Monitor closely for HMG- CoA reductase inhibitor-associated adverse reactions, such as myopathy and rhabdomyolysis.

DF = disoproxil fumarate

a. This table is not all inc

b. ↓ = decrease, ↑ = increase

c. These interactions have been studied in healthy adults.

12.7. Other Events

We will not discontinue study drug for clinical events not thought to be serious drug-related AEs. For example, a hospitalization for clinical worsening may or may not result in cessation of trial participation. Such events could result in missing data for primary and secondary endpoints, comprising the integrity of the analysis. This trial does prohibit certain therapies, thus there may be a reason to stop study drug participation under such circumstances. Even if subjects are withdrawn from the study drug, outcome assessments will continue, allowing analysis by intent-to-treat.

12.8. Safety and Adverse Events

12.8.1. Definitions

Adverse event (AE): Any untoward medical occurrence associated with the protocol procedures, whether or not considered product or process related. Any symptom, sign, illness or experience that develops or worsens in severity during the course of the study. Inter-current illnesses or injuries should be regarded as AEs. Abnormal results of diagnostic procedures are considered to be AEs if the abnormality:

- results in study withdrawal
- is associated with a serious AE
- is associated with clinical signs or symptoms
- leads to additional treatment or to further diagnostic tests
- is considered by the investigator to be of clinical significance

Serious adverse event (SAE): Adverse events are classified as serious or non-serious. A *serious adverse event* is any AE that is:

- fatal
- life-threatening
- requires or prolongs hospital stay
- results in persistent or significant disability or incapacity
- a congenital anomaly or birth defect
- an important medical event

Important medical events are those that may not be immediately life threatening, but are clearly of major clinical significance. They may jeopardize the subject, and may require intervention to prevent one of the other serious outcomes noted above. For example, drug overdose or abuse, a seizure that did not result in in-subject hospitalization or intensive treatment of bronchospasm in an emergency department would typically be considered serious.

All AEs that do not meet any of the criteria for serious should be regarded as *non-serious AEs*.

Suspected adverse reaction: Any adverse event for which there is a reasonable possibility that the drug/investigational product caused the adverse event. For reporting purposes, "reasonable possibility" means there is evidence to suggest a causal relationship between the drug/investigational product and the adverse event.

Unanticipated Adverse Device Effect (ADE): is any serious adverse effect on health or safety, or any life-threatening problem or death caused by, or associated with, a device, if that effect, problem, or death was not previously identified in nature, severity, or degree of incidence in the investigational plan or application, or any

other unanticipated serious problem associated with a device that relates to the rights, safety, or welfare of subjects.

12.8.2. Classifying Adverse Events

Severity

The intensity of the AE is classified according to the CTCAEv4.0.¹⁵ Grade refers to the severity (intensity) of the AE:

- **CTCAEv4 Grade 1:** mild; asymptomatic or mild symptoms; clinical or diagnostic observations only; intervention is not indicated.
- **CTCAEv4 Grade 2:** moderate; minimal, local, or noninvasive intervention is indicated; limiting to age-appropriate instrumental activities of daily living (ADL; instrumental ADL refers to preparing meals, shopping for groceries or clothes, using the telephone, managing money, etc).
- **CTCAEv4 Grade 3:** severe or medically significant but not immediately life threatening; hospitalization or prolongation of hospitalization is indicated; disabling; limiting to self-care ADL (self-care ADL refers to bathing, dressing and undressing, feeding self, using the toilet, taking medications, and not bedridden).
- **CTCAEv4 Grade 4:** life-threatening consequences; urgent intervention is indicated.
- **CTCAEv4 Grade 5:** death due to an AE.

Expectedness

AEs must be assessed as to whether they were expected to occur or were unexpected, meaning not anticipated based on current knowledge found in the protocol, investigator brochure, product insert, or label.

Expected: an AE/ADE known to be associated with the intervention or condition under study.

Unexpected: an AE/ADE for which the nature or severity is not consistent with information about the condition under study or intervention in the protocol, consent form, product brochure, or investigator brochure.

OHRP defines an **unexpected AE** as any AE occurring in one or more subjects participating in a research protocol, the nature, severity, or frequency of which is **not** consistent with either:

- 1) the known or foreseeable risk of AEs associated with the procedures involved in the research that are described in a) the protocol-related documents, such as the IRB-approved research protocol, any applicable investigator brochure, and the current IRB-approved informed consent document, and b) other relevant sources of information, such as product labeling and package inserts; or
- 2) the expected natural progression of any underlying disease, disorder, or condition of the subject(s) experiencing the AE and the subject's predisposing risk factor profile for the AE.

Relatedness

- 1) **Definite:** the AE/ADE is clearly related to the research procedures
- 2) **Probably:** the AE/ADE is likely related to the research procedures
- 3) **Possible:** the AE/ADE may be related to the research procedures
- 4) **Unlikely:** the AE/ADE is doubtfully related to the research procedures
- 5) **Unrelated:** the AE/ADE is clearly not related to the research procedures

For each identified AE/ADE, an entry on the AE/ADE form will be completed. Reporting procedures should be started immediately upon learning of a SAE/ADE.

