Study observations	
 • Laboratory tests including hepatic function panel at screening and at multiple time points during follow-up. • Fibroscan at screening, post-transplant (prior to treating HCV), and post-treatment. • HCV RNA prior to treatment, on treatment, and 4 and 12 weeks after completing Zepatier, Epclusa, or another appropriate antiviral treatment.
Type of control	None
Number of subjects	Estimated 11 HCV-negative subjects transplanted with a lung from an HCV-infected donor
Plan for statistical analysis	Primary endpoint:

	
• Post-treatment sustained virologic response (SVR) 
Secondary endpoints:
 
• Determine if there are major adverse events attributable to HCV therapy in post-lung transplant patients.• Evaluate 1-year lung graft survival in HCV-negative patients who receive a lung transplant from an HCV-positive donor• Determine the rates of spontaneous HCV clearance among HCV-negative patients with lung failure receiving a lung from an HCV-positive donor 
Data analysis:
 
The primary analysis will be based on a calculation of SVR rates (number of subjects with SVR-12; negative HCV RNA 12 weeks after completing Zepatier, Epclusa, or another appropriate antiviral treatment / (number of subjects treated with Zepatier, Epclusa, or another appropriate antiviral treatment post-lung transplantation)

--	---

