5.2. Specific aims

Primary aims:

1. Primary efficacy objective: To determine sustained virologic response (SVR) rates of open-label Zepatier, Epclusa, or another appropriate antiviral treatment in hepatitis C virus (HCV) negative patients who receive a lung transplant from an HCV-infected donor, leading to post-transplantation de-novo HCV infection.
2. Primary safety objective: To determine the safety of administration of open-label Zepatier, Epclusa, or another appropriate antiviral treatment among HCV-negative patients who receive a lung transplant from an HCV-infected donor and develop post-transplant HCV infection.

Secondary aims:

1. To determine 1-year graft survival rates of HCV-negative lung transplant patients who receive a lung transplant from an HCV-infected donor, including those who spontaneously clear HCV and those who receive open-label Zepatier, Epclusa, or another appropriate antiviral treatment upon development of de-novo HCV.
2. To evaluate rates of spontaneous clearance of HCV among HCV-negative patients who receive a lung transplant from an HCV-infected donor.
3. To compare the quality-of-life of HCV-negative patients receiving a lung transplant from a HCV-infected donor to those of similar patients remaining on the waitlist for a standard deceased donor lung transplant.

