9.2.1. Safety

Subject safety and adverse events will be based in CTCAE Version 4 criteria, listed in Section 13, and will include adverse events and serious adverse events, related both to receipt of a lung transplant from an HCV-positive donor among HCV-negative subjects with lung failure, and adverse events related to administration of Zepatier, Epclusa, or another appropriate antiviral treatment.

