10.6. Safety Analysis

All patients will be assessed for toxicity and included in the safety analysis. This analysis will include summaries of the incidence and grade of toxicities. Safety interim analyses will be performed at days 14, 30, 60, 90, 118, and 184, and will be reported at each DSMB meeting. SAEs will be evaluated by the DSMB.

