12.8.3. Interpretation of Definitions

AE Reporting Period

The study period during which AEs must be reported is normally defined as the time of consent to the end of the study treatment follow-up. However, for this study, the AE reporting period will be divided based on the three phases of the study.

a. **Screening phase:** When all screening tests have been done, we will assess for any AEs related to the screening tests at the time of communication with the subject about whether he/she is officially eligible or ineligible for the study.

Preexisting Condition: A preexisting condition is one that is present at the start of the study. A preexisting condition should be recorded as an AE if the frequency, intensity, or the character of the condition worsens during the study period.

b. **Waitlist phase:** We will only capture AEs that are pertinent to the study. Specifically the following will be captured:

1. Patient death,
2. Patient develops a condition that would exclude them from the study,
3. Patient is de-listed (taken off the lung transplant waitlist),
4. Patient is made inactive on the transplant waitlist,
5. Patient is transplanted with a non-HCV lung.

In order to ascertain these events, we will review the patient's medical record once a month, and will contact the patient (by phone, e-mail, or in-person) every 6-8 weeks.

c. **Post-transplant phase:** All AEs will be assessed at every clinic visit when the subject is seen by a member of the study team.

d. **Post-study:** At the last scheduled visit, the investigator will instruct each subject to report any subsequent event(s) that the subject, or the subject's personal physician, believes might reasonably be related to participation in this study.

All unresolved AEs considered possibly, probably or definitely related to the study drug should be followed by the investigator until the events are resolved, the subject is lost to follow-up, or the AE is otherwise explained. The investigator should notify the IRB of any death or AE occurring at any time after a subject has discontinued or terminated study participation that may reasonably be related to this study. The IRB will also be notified if the investigator should become aware of the development of cancer or of a congenital anomaly in a subsequently conceived offspring of a subject that has participated in this study.

General Physical Examination Findings (screening, post-transplant, and post-study phases)

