12.8.4.1. Reporting Process

UPs posing risks to subjects or others as noted above will be reported to local IRB using a Medwatch or CIOMS report of the event (including a description of the event with information regarding its fulfillment of the above criteria, follow-up/resolution and need for revision to consent form and/or other study documentation) will be completed.

All Serious Adverse Events, regardless of causal relationship to the investigational product, will be forwarded to **Merck Worldwide Product Safety** via fax (**[contact]**) within 2 working days of the investigator becoming aware of the event and no later than 3 calendar days.

The Principal Investigator is expected to provide as much of the following information:

- Protocol name and number
- Subject identifiers (no PHI will be shared with the IRB, unless requested)
- Demographic data
- Nature of the event
- Severity of the event
- Probable relationship (causality) of AE to study procedure
- Date and time of AE onset
- Date and time of AE resolution, if available
- Concomitant medications that the participant was taking for an underlying medical condition or disease and the therapeutic agents used for the treatment of the adverse event
 - Clinical assessment of participant conducted at time of SAE/AE
 - Results of any laboratory and/or diagnostic procedures, and treatment
 - Follow-up plan
 - Outcome
 - Autopsy findings (if appropriate)

The Principal Investigator will provide details about the AE/ADE as they become available. If additional information cannot be obtained for whatever reason, this will be documented. The Principal Investigator should inform the IRB when no other information is expected. The Principal Investigator should provide the IRB with a logical, complete, and accurate narrative description of the SAE based upon the above information.

The Principal Investigator should promptly determine an assessment of causality

The IRB determines if any corrective actions should be initiated as a result of any known specific or collective SAE/AE(s) and inform the principal investigator of the corrective action (e.g., revision of informed consent form, protocol, CRF).

The Principal Investigator/designee should keep originals or photocopies of all relevant documentation, including facsimile confirmations, and file them in the participant's file.

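### The plan sets no causality rating for the antiviral separate from the HCV-positive lung, and no treated-recipient safety set or on-treatment window, although its safety objective needs them

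*Combined protocol and SAP*

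**What the plan says.** **What has to be estimated.** The primary safety objective in section 5.2 is "To determine the safety of administration of open-label Zepatier, Epclusa, or another appropriate antiviral treatment among HCV-negative patients" who go on to develop HCV after transplant. The synopsis lists safety among the secondary endpoints: "Determine if there are major adverse events attributable to HCV therapy in post-lung transplant patients". Section 9.2.1 defines the safety outcome as events arising from receipt of the HCV-positive lung "and adverse events related to administration of Zepatier, Epclusa, or another appropriate antiviral treatment".

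**What is recorded.** Section 12.8.2 gives one five-level relatedness scale. It runs from "the AE/ADE is clearly related to the research procedures" to "the AE/ADE is clearly not related to the research procedures", with the same reference at every level. The content list for event reports in section 12.8.4.1 asks for "Probable relationship (causality) of AE to study procedure". Neither term is defined.

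**What is analysed.** Section 10.6 states: "All patients will be assessed for toxicity and included in the safety analysis". Section 10.3 says the same. Both plan summaries of incidence and grade. Neither says whether all patients means consented, transplanted or treated. Neither sets an on-treatment period or a breakdown by relatedness to drug.

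**The concern.** The trial has no control group and plans 11 treated recipients. The drug-safety endpoint therefore depends on investigators' attribution of individual events. If an event carries a single rating against an undefined set of procedures, a rating of related does not say whether the drug, the donor-derived infection or the operation was suspected.

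Hepatic events show the problem. Sections 4.3 and 7.1 name raised liver enzymes among drug-related serious events. Section 12.11.5 says that HCV itself can cause severe acute liver inflammation. One rise in aminotransferases could come from either source.

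Tables of incidence and grade in an unspecified population would not fill the gap. Attribution would then have to be done after the outcomes are known, which is open to bias in an open-label study.

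**Working it through.** The documents give no safety precision, power or event-rate target, so there is no figure of the plan's to reproduce. The check sets the sections side by side and then sizes the consequences.

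**1. Which sections need a drug rating, and which supply one**

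| Section | Reference for causality |
|---|---|
| Synopsis, 5.2 | HCV therapy |
| 9.2.1 | Two streams: HCV-positive lung, and antiviral |
| 12.8.1 (suspected adverse reaction) | Drug or investigational product |
| 12.8.3 (follow-up of unresolved events) | Study drug, at the possible, probable or definite level |
| 12.7 | Serious drug-related events |
| 12.8.2 (the only scale) | Research procedures, undefined |
| 12.8.4.1 (report content) | Study procedure, undefined |

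The first five rows need or presume a drug judgement. The two rows that specify what is written down do not ask for it separately.

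The meaning of the undefined term cannot be settled from the text. The list of research procedures at Visit 1 (8.1.3.3) includes dispensing study drug and omits the transplant. Section 12.11.1 lists the risks of transplant surgery under study procedures, while 12.11.4 puts drug risks under their own heading.

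**2. Why attribution matters here**

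Inputs: 11 treated recipients (Abstract); about 40% readmitted within 30 days (12.11.1); late aminotransferase elevations above 5 times the upper limit in about 1 to 3% on Zepatier (12.5). Independence between subjects is assumed.

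- Expected readmissions: 0.40 × 11 = 4.4.
- Probability of at least one readmission: 1 − 0.60^11 = 99.6%.
- Probability of at least one drug-associated elevation: 1 − 0.99^11 = 10.5% to 1 − 0.97^11 = 28.5%.

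Treatment starts within 4 weeks of transplant (7.1.2), and the schedule in 8.2.1 marks the start at days 2 to 7. The readmission period therefore overlaps early dosing, and some events may precede the first dose. Incidence without attribution would mostly describe transplant complications. These figures show why a separate rating is useful. They do not measure the defect in the scale.

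**3. Denominator**

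Spontaneous clearers stay in follow-up untreated and are replaced (8.1.3.6, 9.2.3), so more may be transplanted than treated. The documents do not say how many; 13 is assumed for illustration. Intervals are exact (Clopper-Pearson), two-sided 95%, which is also an assumption because the plan names no interval.

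- Treated recipients: 1/11 = 9.1% (0.2 to 41.3).
- Transplanted recipients: 1/13 = 7.7% (0.2 to 36.0).
- No events among 11 treated: upper limit 28.5%.

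The difference between 9.1% and 7.7% is small beside either interval.

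**The case against.** The strongest reply is that the protocol does not ignore drug causality. Section 12.8.1 defines a suspected adverse reaction against the drug, and the reporting table in 12.8.4 uses that term. Section 12.8.3 applies the upper three levels of the same scale to the study drug. Section 9.2.1 keeps the two sources apart. An investigator might well rate against the drug in practice, and the adverse event form, which is not in the documents, may already have a field for it. This stands in part. The gap is a mismatch between sections and a missing specification, not a total absence of drug attribution.

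A reader might infer three stronger things, none of which the documents support:

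- **That drug safety cannot be isolated at all.** Event entries and dosing records would allow a treated-only, post-dose summary to be built. It is not prespecified, and attribution would be retrospective.
- **That the rating necessarily merges organ and drug.** The term is undefined, and the sections point in different directions.
- **That rates would be diluted to between 1/20 = 5.0% and 1/35 = 2.9%.** This takes all patients to mean everyone consented or enrolled (20-30 and 25-35, both in section 6.1). It is the least plausible reading. Section 6.1 calls the transplanted group the population of interest. Waitlisted patients have only five event types captured, such as "Patient is transplanted with a non-HCV lung", and section 12.8.3 already separates them by phase.

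It is also fair to say that two ratings will not remove confounding in an uncontrolled study. They make the judgement explicit and record it at the time of the event.

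**Conclusion.** The point holds as a gap in specification. The objective, the endpoint and the follow-up rule need attribution to the drug, and section 9.2.1 also wants organ-related events. The defined scale and the report item do not record the two separately. The planned analysis then gives incidence and grade in an undefined population, with no treated set, on-treatment window or table by drug-relatedness. The plan as written does not deliver the drug-attributable endpoint.

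The numerical effect of the population wording is minor if all patients means transplanted recipients. That conclusion rests on the assumed 13 transplanted. The more important loss is attribution. No figure in the documents is wrong, and no clinical management is affected. The change is worth making because it is cheap and because attribution is the main route to this endpoint in 11 uncontrolled subjects.

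**What to change.** **Sections 12.8.2 and 12.8.4.1.** Rate each post-transplant adverse event twice on the existing five-point scale: once for relation to the antiviral regimen, and once for relation to receipt of the HCV-positive lung, including donor-derived HCV.

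**Sections 10.3 and 10.6.**

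- Define the antiviral safety set as recipients with at least one antiviral dose.
- Count events from first dose to a prespecified end, for example the SVR-12 assessment. Without an end, up to a year of transplant complications would enter the drug table.
- Tabulate by grade and drug-relatedness, with exact 95% intervals.
- Give a second table for all transplanted recipients over the full follow-up.

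**Cost.** One extra field on the adverse event form, if the form follows the current scale, and one extra table. The intervals will be wide, as the 1/11 example shows, and should be reported as such.
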